1.1 Diffuse Large B-cell Lymphoma and Unfit/Frail Patients

Diffuse large B-cell lymphoma (DLBCL) is the most frequently diagnosed non-Hodgkin's lymphoma (NHL) with more than one-third of patients 75 years or older at diagnosis. In general, patients who are ≥ 75 years face unique treatment challenges and experience poor outcomes due to a number of factors including unfavorable disease biology, comorbidities, and an inability to tolerate standard first-line therapy. Additionally, up to 25% of older adults with DLBCL do not receive any first-line therapy and this number is even higher in patients ≥ 75 years of age or in patients with poor performance status (Di, 2021). There is also a significant heterogeneity in how older patients are evaluated for fitness and ability to tolerate therapy. The current American Society of Clinical Oncology (ASCO) guidelines recommend a comprehensive geriatric assessment for all older patients > 65 years of age, however, very few studies in patients with DLBCL required a geriatric assessment tool for inclusion or to inform treatment choice (Tavares & Moreira, 2021). The simplified geriatric assessment (sGA) developed by the Fondazione Italiana Linfomi (FIL) identifies three distinct categories (fit, unfit, and frail) based on age, activities of daily living (ADL), instrumental activities of daily living (IADL) and the Cumulative Illness Rating Scale for Geriatrics (CIRS-G) (Merli, 2021; Katz, 1963; Parmelee, 1995; Lawton, 1969)

In all age groups, including patients ≥ 75 years who are fit, standard first-line therapy consists of immuno-chemotherapy, such as R-CHOP (rituximab, cyclophosphamide, doxorubicin, vincristine, and prednisone) (NCCN Guidelines, 2021). Unfit patients, defined (per sGA) as ≥ 80 years of age with co-existing medical conditions are often unable to tolerate full-dose R-CHOP. The current recommendation in this patient population favors the use of R-mini-CHOP (50% of R-CHOP dose) as a compromise between efficacy and safety (Peyrade, 2011). In the SENIOR study by Oberic (2021), the overall response rate (ORR) was 73% and the complete response (CR) rate was 53% with a 2-year progression-free survival (PFS) of 56% in patients who received R-mini-CHOP. Olszewski (2021) reported an ORR of 61.5% and CR rate of 43.5% with single-agent mosunetuzumab, a CD20 \times CD3 T-cell engaging bispecific, was reported in a similar patient population. Frail patients, defined per sGA, who are ≥ 80 years of age with more significant co-existing medical conditions are often unable to tolerate R-mini-CHOP and have no definitive standard of care (SoC) (Morrison, 2020). There is an additional population of patients who are > 65 years of age with cardiac comorbidities that preclude the use of an anthracycline-containing regimen and for which there is no SoC (Hitz, 2016; Moccia, 2021). Recent studies in patients who are unable to tolerate anthracycline-containing regimens demonstrate an ORR of approximately 61% and a CR rate of 29.5% to 53% with a 2-year PFS between 38% to 49.8% (Fields, 2014; Storti, 2018). There remains an unmet need to improve outcomes for these patients by incorporating novel agents into effective regimens with improved safety when compared to existing SoC.

Loncastuximab tesirine (ADCT-402) is an antibody-drug conjugate (ADC) directed against human cluster of differentiation 19 (CD19) that is well tolerated and has been shown to have antitumor activity in patients with relapsed or refractory (R/R) DLBCL, with ~48% of adult patients having a response.

In LOTIS-1, a Phase 1 dose-finding and expansion study in R/R NHL, there were 27 patients with R/R DLBCL who were \geq 75 years of age with an ORR of 55.6% across all dose levels.

In LOTIS-2, a pivotal Phase 2 single-arm study in patients with R/R DLBCL, there were 21 patients who were \geq 75 year of age with an ORR of 52.4% and a CR of 38.1%.

The addition of rituximab is based on preclinical evidence that the addition of rituximab to anti CD19 ADC therapy may result in prolonged tumor control (Ryan, 2017) and on clinical studies showing that the addition of rituximab to standard chemotherapy regimens (e.g., CHOP, GemOx [gemcitabine and oxaliplatin]) improves efficacy (Corazzelli, 2009; Habermann, 2006). As the pyrrolobenzodiazepine (PBD) component of loncastuximab tesirine produces cell death via deoxyribonucleic acid (DNA) damage in a fashion similar to many cytotoxic chemotherapy agents, the addition of rituximab is expected to produce a similar improvement in outcome and potentially result in prolonged tumor control. Rituximab will be given at the standard dose every 3 weeks (Q3W) to coincide with the administration schedule for loncastuximab tesirine to minimize the burden of therapy. This combination is also being explored in a Phase 3 randomized study in patients with R/R DLBCL (LOTIS-5; NCT04384484).

1.2 Description of the Study Drugs

1.2.1 Loncastuximab Tesirine

Loncastuximab tesirine (ADCT-402) is an ADC, composed of a humanized monoclonal antibody (RB4v1.2) directed against human CD19 conjugated through a cathepsin-cleavable linker to SG3199, a PBD dimer cytotoxin. The toxin SG3199 attached to the linker is designated as SG3249.

Pyrrolobenzodiazepines are a class of naturally occurring antitumor antibiotics found in Streptomyces. Pyrrolobenzodiazepine monomers bind in the DNA minor groove and form a single covalent aminal linkage to the exocyclic N2-amino group of guanine within purine-guanine-purine sequences. Pyrrolobenzodiazepine dimers, obtained by joining two PBD monomers together via an appropriate polymethylene tether, have the ability to produce two covalent bonds forming highly cytotoxic DNA interstrand crosslinks (Hartley, 2011).

The schematic representation of loncastuximab tesirine is presented in [Figure 1](#).

[figure not shown]

Figure 1 Schematic Representation and Chemical Structure of Loncastuximab Tesirine

Abbreviations: Ala, alanine; mAb, human monoclonal antibody being studied (RB4v1.2); PABC, para-aminobenzyl carbamate; PEG, polyethylene glycol; Val, valine.

1.2.2 Rituximab

For rituximab or rituximab biosimilar or subcutaneous (s.c.) rituximab formulation, refer respectively to each United States Package Insert (USPI) for detailed information including safety and efficacy.

1.3 Loncastuximab Tesirine - Clinical Results

1.3.1 Phase 1 Study, ADCT-402-101

ADCT-402-101 (NCT02669017) is a first-in-human Phase 1 dose-escalation study of loncastuximab tesirine in R/R B-NHL patients, who have failed or are intolerant to established therapies, or have no other treatment options available. The study was completed with 183 patients enrolled.

[figure not shown]
Toxicity was manageable. The most common (observed in at least 5% of patients) Grade ≥ 3 treatment-emergent adverse events (TEAEs) were gamma glutamyl transferase (GGT) increased (21.3%); neutropenia (16.9%); anemia (15.3%); neutrophil count decreased (14.8%); thrombocytopenia (12.0%); platelet count decreased (10.4%). The TEAEs in 35 (19.1%) patients led to treatment discontinuation. Dose-limiting toxicities (DLT) were reported in 4 patients (3 thrombocytopenia and 1 febrile neutropenia).

Out of 180 evaluable patients with B-NHL, 48 (26.7%) achieved CR and 34 (18.9%) achieved partial response (PR), for an ORR of 82/180 (45.6%). Out of 137 evaluable patients with DLBCL, 32 (23.4%) achieved CR and 26 (19.0%) achieved PR, for an ORR of 58/137 (42.3%). Out of 14 evaluable patients with FL, 9 (64.3%) achieved CR and 2 (14.3%) achieved PR, for an ORR of 11/14 (78.6%). Out of 15 evaluable patients with mantle cell lymphoma (MCL), 5 (33.3%) achieved CR and 2 (13.3%) achieved PR, for an ORR of 7/15 (46.7%).

[figure not shown]
1.3.2 Phase 2 Study, ADCT-402-201

Study ADCT-402-201 is a Phase 2 study to evaluate the efficacy of loncastuximab tesirine used as monotherapy in patients with R/R DLBCL. The study determines the ORR according to the 2014 Lugano Classification, as well as evaluate the duration of response (DoR), CR, survival, safety, pharmacokinetics (PK), and health-related quality of life (HRQoL).

CCI

[figure not shown]
CCI

CCI

CCI

CCI

Additional details may be found in the current loncastuximab tesirine investigator's brochure (IB).

1.4 Benefit/Risk Assessment

Although R-mini-CHOP has anticancer activity in patients with untreated DLBCL who are unfit for full-dose R-CHOP, there is a need for regimens with an improved safety profile and better CR and PFS. In addition, there is no current SoC for patients who are frail and/or ineligible for anthracycline-based therapy. The combination of loncastuximab tesirine and rituximab is expected to provide an increased anti-tumor response however, the efficacy and safety of this combination in untreated unfit/frail patients has not been established.

More detailed information about the known and expected benefits and risks and reasonably expected adverse events (AEs) of loncastuximab tesirine may be found in the current IB.

2 Study Rationale

Loncastuximab tesirine is an ADC that has been designed to target and kill CD19-expressing malignant B-cells. The Phase 1 study of loncastuximab tesirine in R/R B-cell NHL shows significant activity of loncastuximab tesirine with an acceptable safety profile in patients with R/R DLBCL, FL, and MCL ([Section 1.3.1](#)). The Phase 2 study results verified the efficacy and durability of response in heavily pretreated patients with DLBCL and was well-tolerated when administered in repeated 3-week cycles at 150 µg/kg for the first two cycles and 75 µg/kg for the subsequent cycles ([Section 1.3.2](#)). A Biologics License Application of loncastuximab tesirine for R/R DLBCL was approved by the Food and Drug Administration (FDA) on 23 April 2021.

As illustrated above, loncastuximab tesirine has single agent activity against B–NHL subtypes, including transformed lymphoma, with significant proportion of disease response in DLBCL, including complete remission. The disease course of Grade 3b FL resembles that of DLBCL and should be treated accordingly ([Salaverria & Siebert, 2011](#)). Patients with Grade 3b FL with a significant diffuse component have inferior survival outcomes similar to that of DLBCL ([Hans, 2003](#)). These patients are often excluded from clinical trials and most treatment recommendations are based on retrospective data and small case studies; the curative potential of combination chemoimmunotherapy in Grade 3b FL remains unclear ([Barraclough, 2021](#)). Including this subset of patients is consistent with current international clinical practice guidelines that identify Grade 3b FL as an aggressive lymphoma and recommend immediate treatment similar to that of DLBCL ([Barraclough, 2021](#); [Dreyling, 2020](#); [NCCN Guidelines, 2021](#)). The hypothesis is that loncastuximab tesirine in combination with rituximab may potentially have improved efficacy & safety for 1st line treatment in unfit/frail patients with DLBCL.

2.1 Rationale for Study Design

This is a Phase 2, multi-center adaptive design study with two parallel cohorts which will enroll in total approximately 80 unfit or frail patients with previously untreated DLBCL (respectively Cohort A and Cohort B, n = 40 patients each). The primary objective will be to determine the safety and efficacy of loncastuximab tesirine in combination with rituximab (Lonca-R) in this patient population.

An analysis for efficacy and safety in Cohorts A and B (n = 40 each) as assigned by sGA ([Merli, 2021](#)) will be conducted. The sGA is a validated objective tool to assess fitness status to predict overall survival in older patients with DLBCL.

A response-adapted approach for both cohorts will be utilized where patients in the unfit & frail cohorts who achieve a CR after 3 cycles of therapy will receive one additional cycle of therapy (4 cycles total). Patients in the unfit cohort (Cohort A) who achieve a PR after 3 cycles of therapy will receive 3 additional cycles of therapy (6 cycles total). Patients in the frail cohort (Cohort B) who achieve a PR/stable disease (SD) will receive 3 additional cycles of therapy (6 cycles total). In the patient population being evaluated, de-escalating therapy to a total of 4 cycles in patients who achieve a CR may minimize toxicity while preserving efficacy. End of

treatment CR was recently found to be highly predictive for PFS and OS in DLBCL after first-line immunochemotherapy ([Kostakoglu, 2021](#)).

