	
• CR rate according to the 2014 Lugano Classification criteria• Tolerability: Percentage of patients completing a total of 4 cycles of therapy divided by the total number of patients.
	Secondary Endpoints
	Cohort A and B
	
• ORR according to the 2014 Lugano Classification• 2-yr PFS• 3-yr overall survival (3-yr OS)• Duration of response (DoR)• Frequency and severity of adverse events (AEs) and serious adverse events (SAEs)• Changes from baseline in safety laboratory variables, vital signs, physical examinations, Eastern Cooperative Oncology Group scale of performance status (ECOG PS)• Concentrations and PK parameters of loncastuximab tesirine pyrrolobenzodiazepine (PBD)-conjugated antibody, total antibody, and SG3199 unconjugated warhead• Frequency of confirmed positive anti-drug antibody (ADA) responses, their associated titers and, if applicable, neutralizing activity to loncastuximab tesirine after treatment with loncastuximab tesirine when given in combination with rituximab• Changes in patient-reported outcomes (e.g., symptoms, functions, and overall health status) from baseline as evaluated by Functional Assessment of Cancer Therapy - Lymphoma (FACT-Lym)
	Exploratory Endpoints
	CC1
Study Design:	
This is a Phase 2, multicenter, multi-cohort, open-label study of Lonca-R in unfit/frail patients with previously untreated DLBCL. Fitness and frailty of the patients will be assessed using the sGA tool developed by the FIL. A response-adapted approach will be used in this study. Two parallel cohorts will enroll patients; Cohort A will enroll unfit patients and Cohort B will enroll frail patients or patients with cardiac comorbidities.
 
A treatment cycle in the study is defined as 3 weeks (i.e., 21 days). Cohort A will assess efficacy and Cohort B will assess the efficacy and tolerability of Lonca-R.

After completion of 3 cycles of Lonca-R treatment, patients who achieve CR or PR will continue to receive 1 additional cycle or 3 cycles of Lonca-R, respectively. Patients in Cohort A who do not achieve a CR or PR will discontinue study treatment. For Cohort B only, patients who achieve stable disease (SD) and derive clinical benefit per the treating physician may continue to receive additional 3 cycles of Lonca-R.

Based on the results from Cohort A and/or B, a protocol amendment will be considered to further evaluate the Lonca-R combination in these patient populations.

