8. Pregnancy test will be limited to females of childbearing potential; a final pregnancy test should be performed ≥ 12 months after the last dose of study drug has been administered (remote testing may be performed).
9. For days of loncastuximab tesirine infusion, PK will be collected predose (preferably within 2 h prior to start of infusion), and at the end (within -5 to +10 min) of Lonca infusion.
10. ADA samples will be collected predose (preferably within 2 h prior to start of infusion) on C1D2, C2D1 and then every other cycle beginning with C4. Patients who test positive for ADAs may be requested to supply additional ADA samples.

CCI

12. PRO instrument should be completed prior to clinical assessment.
13. Patients in both cohorts will receive 1 additional cycle of assigned therapy (Cycle 4) if in CR and 3 additional cycles if PR (Cycles 4-6) based on PET-CT after Cycle 3. Patients in cohort B who achieve stable disease and are receiving clinical benefit may receive 3 additional cycles (Cycles 4-6).
14. Premedication for the Lonca-R regimen consists of dexamethasone 4 mg PO/IV BID $\times 3$ days beginning the day prior to loncastuximab tesirine; premedication(s) for rituximab will be given according to institution standard.

Visit Scheduling Windows:

- Treatment Period: C1D1 is the reference day, otherwise visit day ± 2 days, except of visit day 2 where the time window is +2 days.
- EoT: Patients who complete all assigned treatment cycles of treatment should have their EoT visit performed 28 (± 7) days from the last dose of study treatment, and in any case prior to the initiation of new anticancer treatment.
- Follow-up Period: visit day ± 14 days.

1 Introduction and Background

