2.2 Rationale for Dose Selection

In the pivotal monotherapy Phase 2 study for R/R DLBCL, ADCT-402-201, loncastuximab tesirine was dosed every 3 weeks, with 150 µg/kg for first two cycles and 75 µg/kg for the subsequent cycles, which resulted in a high level of efficacy and was well tolerated. In addition, PK analyses show that this dosing regimen resulted in comparable exposure between Cycle 1 and subsequent cycles and that this dosing regimen resulted in consistent drug exposure across cycles. The dosing regimen chosen for this study is based on the regimen of loncastuximab tesirine used in the Phase 2 study. This study will utilize the same dosing regimen for Lonca-R as the ongoing Phase 3 clinical trial LOTIS-5 comparing the Lonca-R regimen (after a safety run-in) to R-GemOx in 2L transplant-ineligible patients with DLBCL. Treatment-naïve patients will present with levels of lymphocytes (within normal limits) which are believed to function as an antigen sink to loncastuximab tesirine. Administration of rituximab is known to reduce lymphocytes levels within a day ([Blasco, 2009](#)). Therefore, loncastuximab administration in Cycle 1 is given 1 day (+2 days) after rituximab administration.

3 Study Objectives and Endpoints

Table 3 Study Objectives and Endpoints

Objectives	Endpoints
Primary	
Cohort A To assess the efficacy of a response-adapted treatment of Lonca-R in unfit patients with previously untreated DLBCL or HGBCL or Grade 3b FL.	(Co-)Primary Endpoints: Cohort A CR rate, defined as proportion of patients with a BOR of CR according to the 2014 Lugano Classification criteria (Appendix 12.2). Cohort B 
• CR rate, defined as proportion of patients with a BOR of CR according to the 2014 Lugano Classification criteria.• Tolerability as defined by the percentage of patients completing a total of 4 cycles of therapy divided by the total number of patients.
Secondary	

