4.1 Overview

This is a Phase 2 open-label, study of Lonca-R in previously untreated unfit/frail patients with DLBCL. The study will include a Screening Period (up to 28 days), a Treatment Period (4-6 cycles [each of 3 weeks]), and a Follow-up Period (for up to 5 years after treatment discontinuation) ([Section 4.2](#)).

A response-adapted approach will be used in this study. Two parallel cohorts will enroll patients in the study. Cohort A will enroll unfit patients and Cohort B will enroll frail patients or patients with cardiac comorbidities. Cohort A will assess efficacy and Cohort B will assess the efficacy and tolerability of Lonca-R. Fitness and frailty of the patients will be assessed based on the sGA tool developed by the FIL ([Merli, 2021](#)). See [Section 7.2](#) for details about sGA.

The study will enroll approximately 80 patients (approximately 40 patients in each cohort).

Based on the results from Cohort A and/ or B a protocol amendment will be considered to further evaluate the Lonca-R combination in these patient populations.

Enrolled patients in both cohorts will receive Lonca-R for 3 cycles. Patients who achieve CR after 3 cycles of Lonca-R treatment will continue to receive one additional cycle of Lonca-R. Patients who achieve PR after 3 cycles of Lonca-R will continue to receive additional 3 cycles of Lonca-R. Additionally, for Cohort B only, patients who achieve SD and derive clinical benefit per the treating physician may also continue to receive additional 3 cycles of Lonca-R. Details of dosing regimen are described in [Section 6.3 \(Table 4\)](#), (see [Figure 2](#)).

The duration of the study participation for each patient is defined as the time from the date of signed written informed consent to the completion of the follow-up period, withdrawal of consent, loss to follow-up, or death, whichever occurs first. Each patient enrolled in both cohorts will have the same duration of study participation.

18 weeks) or unacceptable toxicity, or other discontinuation criteria (see [Section 5.5](#)), whichever occurs first. Details of the treatment regimen are described in [Table 4](#).

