5.5.1 Discontinuation from Study Treatment

A patient may be discontinued from the study treatment for any of the following reasons:

- Adverse event
- Patient decision
- Investigator decision
- Major protocol deviation
- Lost to follow-up
- Disease progression (radiographic or clinical)
- Study termination by the Sponsor

- For Cohort A, patients who did not achieve a CR or PR after 3 cycles
- For Cohort B, patients who do not achieve a CR or PR or SD after 3 cycles
- Other

A patient with any of the following reasons will be immediately discontinued from study treatment:

- Pregnancy
- Death

IMPORTANT: Study treatment discontinuation is not equivalent to discontinuation from the study. Patients discontinuing the study treatment will be asked to perform an EoT visit ([Section 4.2.3](#)) and continue with the Follow-up period ([Section 4.2.4](#)) as per protocol.

The investigational site should make every effort to complete follow-up per protocol. If patients are unable to return to the site, patient status, including but not limited to survival status, may be obtained by site staff via phone, email, or mail.

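### Protocol 2.1 conflicts with four other passages on continuing Cohort B patients with stable disease; separately, the 4-cycle tolerability co-primary counts response-rule stops as failures

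*Protocol*

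**What the plan says.** **Continuation with SD in Cohort B.**

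- Protocol 2.1 groups SD with PR and attaches no condition: "Patients in the frail cohort (Cohort B) who achieve a PR/stable disease (SD) will receive 3 additional cycles of therapy (6 cycles total".
- Protocol 4.1 makes it optional and conditional: "for Cohort B only, patients who achieve SD and derive clinical benefit per the treating physician may also continue to receive additional 3 cycles".
- The synopsis agrees with 4.1: "patients who achieve stable disease (SD) and derive clinical benefit per the treating physician may continue to receive additional 3 cycles of Lonca-R". SAP 3.1 carries the same rule.
- Table 2 footnote 13 is also conditional, but does not say who judges the benefit: "Patients in cohort B who achieve stable disease and are receiving clinical benefit may receive 3 additional cycles (Cycles 4-6".
- Protocol 5.5.1 gives this response-based reason for stopping: "For Cohort B, patients who do not achieve a CR or PR or SD after 3 cycles". SD without clinical benefit has no entry of its own. The list is permissive, however, and also contains the investigator's decision and an open category.

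**Endpoint.** Protocol Table 3 defines the second Cohort B co-primary: "Tolerability as defined by the percentage of patients completing a total of 4 cycles of therapy divided by the total number of patients". It makes no separate provision for patients whom the response rule takes off treatment after Cycle 3.

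**SAP.** Section 2.1 keeps tolerability among the Cohort B primary objectives. Section 4.8 names CR rate, ORR and duration of response as the efficacy endpoints. Section 4.7.1 summarises the total number of cycles dosed. No section sets out a 4-cycle completion rate, and Section 3.4 records no modification to the protocol's statistical section.

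**The concern.** There are two separate matters.

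The first is wording. For a Cohort B patient with SD at the scan before Cycle 4 who is judged not to be benefiting, Protocol 2.1 prescribes Cycles 4 to 6, while the other four passages let treatment end at 3 cycles. Two sites could treat the same patient differently and each cite the protocol.

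The second is the endpoint, and it remains whichever SD rule is adopted. A patient who stops after Cycle 3 because the disease has not responded cannot complete 4 cycles, yet stays in the denominator. The rate labelled tolerability therefore mixes lack of response with intolerance. In a frail cohort, where tolerability is a co-primary question, a reader would want to know how many non-completers stopped for each reason. If SD stops are recorded under the investigator's decision or the open category, the planned disposition table would not separate them from unrelated stops.

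**Working it through.** **1. The plan's own figures.** The only precision figures are the exact intervals for the CR rate at n = 40 (Protocol Table 7, SAP 3.2). With x responders, the Clopper-Pearson 95% limits are the 2.5% quantile of Beta(x, n − x + 1) and the 97.5% quantile of Beta(x + 1, n − x). These give 16.6–46.5 for 12/40, 24.9–56.7 for 16/40, 33.8–66.2 for 20/40 and 43.3–75.1 for 24/40. All match. No target or precision is given for tolerability.

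**2. Where the readings diverge.**

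| Cohort B patient after Cycle 3 | Protocol 2.1 | Synopsis, Table 2, Protocol 4.1, SAP 3.1 | Can complete 4 cycles? |
|---|---|---|---|
| SD, benefiting, continued | continues | may continue | yes, under both |
| SD, not continued | continues | stops at 3 cycles | only under 2.1 |
| Progression, stopped | stops | stops | no, under both |

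Only the second row depends on the wording. The third row, and the second row under the conditional rule, are response-rule stops that the endpoint scores as failures.

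**3. Effect per patient.** Rate = completers / all patients. One patient is worth 1/40 = 2.5 points at the planned size. SAP 3.2 gives 41 treated patients in total without a split by cohort. If Cohort B had 20 patients (an assumption), one patient would be worth 1/20 = 5 points.

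**4. Range for the wording.** The documents give no SD share, so assume 5%, 10% or 20% of 40, that is 2, 4 or 8 patients. Assume also 24 completers among the patients without SD. Exact 95% intervals are in brackets.

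| SD patients | None continue | Half continue | All continue and complete Cycle 4 | Largest gap |
|---|---|---|---|---|
| 2 | 24/40 = 60.0% (43.3–75.1) | 25/40 = 62.5% (45.8–77.3) | 26/40 = 65.0% (48.3–79.4) | 5 points |
| 4 | 24/40 = 60.0% (43.3–75.1) | 26/40 = 65.0% (48.3–79.4) | 28/40 = 70.0% (53.5–83.4) | 10 points |
| 8 | 24/40 = 60.0% (43.3–75.1) | 28/40 = 70.0% (53.5–83.4) | 32/40 = 80.0% (64.4–90.9) | 20 points |

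The gap is the number of SD patients not continued divided by 40, whatever the base count, provided each would have completed Cycle 4.

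**5. What a split would show.** Take 4 SD patients, none continued. The endpoint as defined reports 24/40 = 60.0% and 16 failures. Split by reason, 4 of the 16 (10.0% of 40) stopped under the response rule and 40 − 24 − 4 = 12 (30.0%) stopped for other reasons. The headline rate is unchanged, but its interpretation is not.

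**The case against.** The strongest reply is that four passages agree and the exception is a sentence in a rationale section. A site would more naturally follow the Schedule of Events. Protocol 5.5.1 does not force continuation either, since its permissive list would let even a site following 2.1 stop the patient. This stands: the conflict is narrow, although agreement among four passages does not remove it.

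The 5 to 20 points are also a ceiling. The conditional rule does not imply that no SD patient continues, and not every frail patient who continues would complete Cycle 4. This stands too.

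The study was discontinued on 20 July 2023, and SAP 1 warns that not all protocol analyses are covered, so rewording cannot change how patients were treated. That is correct, and it lowers the severity. It does not settle the reporting question. SAP 2.2 names PFS, OS and patient-reported outcomes as examples of what will not be analysed, for lack of follow-up. Tolerability is not among them and does not need that follow-up.

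Much of the information is already due in the disposition, exposure and tumour-assessment listings (SAP 4.2, 4.7.1, 4.8). That keeps the fix cheap, but nothing in the SAP brings these items together.

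A reader might go further and infer that the CR co-primary also turns on the wording, because a continued patient has a scan at the end of Cycle 6. The documents do not support this. CR is the best response up to subsequent therapy (Protocol 9.7.1), and patients who stop for reasons other than progression or new therapy still have imaging every 12 weeks in the first year (Protocol 7.3). A later CR can be recorded in them, and the documents give no basis for sizing any difference.

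**Conclusion.** The point holds in two limited parts. Protocol 2.1 is inconsistent with the synopsis, Table 2 footnote 13, Protocol 4.1 and SAP 3.1, with consequences only for SD patients who are not continued. A reader might infer that the wording decides the endpoint for every SD patient; it does not, since one who continues can complete 4 cycles under either text. Independently of that wording, the tolerability co-primary scores response-rule stops after Cycle 3 as failures and so does not measure tolerability alone.

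The size is 2.5 points per affected patient at n = 40. The 5 to 20 points for the wording are an upper bound resting on assumed SD shares of 5% to 20%, with none continuing on one side and all continuing and completing Cycle 4 on the other. The number of progression stops is likewise not stated.

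Severity is minor to moderate: the trial has ended early and what remains is how the result is reported. The more useful half of the finding is that the SAP retains the tolerability objective, declares no modification, and contains no analysis of the co-primary endpoint attached to it.

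**What to change.** 1. Reconcile Protocol 2.1 with the synopsis, Table 2 footnote 13, Protocol 4.1, the 5.5.1 list and SAP 3.1 to one rule chosen by the sponsor. No view is offered here on which rule that should be.
2. Add the Cohort B 4-cycle completion analysis to the SAP as the protocol defines it: completers over all patients, with an exact 95% interval to match the CR rate.
3. Add a supplementary row, on the same denominator, that separates patients stopped after Cycle 3 by the response rule (SD not continued, or progression) from those stopped for intolerance, with remaining reasons shown apart.
4. List each Cohort B patient with SD at the scan before Cycle 4, with the decision taken and its reason.

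The cost is a wording correction, one table and one listing, from data already collected. The drawback is that the supplementary row will rest on small numbers and should be read descriptively.
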